A.4) The Screener is the tool CHWs will use to comprehensively and efficiently identify barriers to COPD self-management and disease control. Most items on the current SAMBA screener are applicable to chronic illness self-management and include costs of medications and medical care, mental health disorders like anxiety and depression, alcohol and other substance use disorders, tobacco use, physical and cognitive impairment, social support, and environmental factors (e.g., stable housing, exposure to second hand tobacco smoke). Inhaler technique, controller medication adherence, and action plans are also relevant to COPD patients. Unique COPD items will include behaviors pertaining to oxygen use and exercise, acceptance of influenza and pneumococcal pneumonia vaccines, and beliefs about COPD illness and medications. The screener is implemented after the RA enrolls a participant in the study. The screener is only used for participants in the intervention group.

B. Phase II will focus on intervention implementation and evaluation (months 13-36). We will randomize 58 COPD patients (29 per arm) to the SaMBA-COPD intervention or an attention control and follow them for 9 months to assess health and self-management behavior (SMB) outcomes.

B.1) CHW Training. Training will cover the basics of COPD pathophysiology and treatments and COPD SMB. It will also review the procedures of the SaMBA-COPD model and core skills, including motivational interviewing, communication with healthcare providers, and other topics. After training, CHWs will engage in observed role play until they have mastered the basic

	Protocol Name:	Comprehensive Home-based Self-management Support for COPD Patients
	Principal Investigator:	[name], MPH
	Primary Contact Name/Contact Info:	[name]; [contact]; [contact]
	Date Revised:	4/16/21
	Study Number:	STUDY-18-01345

elements of the protocol. They will then work with actual patients during pre-testing. CHWs will be observed in the field and must be certified before they can provide support to patients independently as was required for SAMBA. Supervisors will do monthly field observations to ensure that quality is maintained.

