- Rather than bringing the Principal Investigator or other licensed clinician into the room to meet with the participant in person, the clinician will be contacted via phone and, with the participant's permission, will be given access to join the video conference and conduct an additional assessment via this platform.
- If the clinician determines that that participant is at elevated risk for suicide, the patient is notified by the clinician that 911 will be called and that this will result in an ambulance being sent to their residence to make sure that the subject is okay. The study coordinator remains on the telephone with the patient until the ambulance arrives. The 911 operator is notified if the patient ends the video conferencing call abruptly or hangs up.

	Protocol Name:	Comprehensive Home-based Self-management Support for COPD Patients
	Principal Investigator:	[name], MPH
	Primary Contact Name/Contact Info:	[name]; [contact]; [contact]
	Date Revised:	4/16/21
	Study Number:	STUDY-18-01345

e. Randomization. Randomization will occur immediately after the baseline interview is complete. To obtain the assignment, the RA will access an online program in REDCap that implements the algorithm.

f. Control Arm. The attention control is designed to isolate the impact of screening for self-management barriers, targeted self-management support, and HBEP. The attention control will consist of 3 visits by a CHW to the home to review the COPD education booklet (COPD 1-2-3). During the first visit, this CHW will review the COPD 1-2-3 booklet in its entirety with the patient. During visits 2 and 3, the CHW will make a visit to "check in" with the patient, ask how they are doing with their respiratory symptoms, and review any sections of the COPD 1-2-3 booklet the patient chooses. The CHW will recommend visits every 2 months but the patient and CHW may choose to modify the interval as needed. If the patient appears to be experiencing worsening respiratory symptoms during any visit, the CHW will notify the patient's physician.

g. Quantitative Data Collection. Baseline, 6- and 9-month interviews will be in-person or over the phone in English or Spanish. Bilingual RAs will conduct them at home or in clinical spaces, by patient preference, using laptop computers and REDCap software, as we do with all of our research.

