i. **Qualitative Data Collection and Analysis.** We will conduct semi-structured exit interviews with patients and CHWs to assess feasibility and perceptions of SaMBA-COPD to guide refinement. Interviews will follow the month 9 interview or at study dropout (30-45 minutes; compensation, \$20). Topics will include satisfaction, burden (physical, emotional, social), convenience, perceived positive or negative effects, and appropriateness. At trial completion, we will conduct qualitative interviews with CHWs and their supervisor and PR staff and physicians to assess the same topics. All interviews will be audio/video-recorded. These interviews will be used for internal evaluation and quality improvement.

j **Quantitative Data Analysis.**

Primary analyses. We will analyze outcomes on the intention-to-treat principle. The primary outcomes are CAT score, ICS technique, and PAAQ scores at 9 months.

Description of Data that Will Be Collected Including Long-Term Follow-Up

Disease beliefs: will be measured with the brief Illness Perceptions Questionnaire (IPQ; available in English and Spanish) that includes items for each of the 5 cognitive domains of the SRM.(15) Medications Beliefs: We will use the Beliefs about Medicines Questionnaire, an English and Spanish validated 10-item scale that measures beliefs about controller medication in 2 subdomains: necessity and concerns (reliability: 0.80). (16) Items will be added to assess expectations of benefits and emotional representations about medications (worried about side effects or addiction, upset about medication regimen, etc.).

Adherence: COPD controller medication adherence, electronically measured: Objective measurement using the Smartinhaler electronic device for metered dose inhalers (MDIs) and the Smartdisk for dry powder inhalers (DPIs) for 4 weeks after each research interview. RAs will attach the monitoring device to the inhaler, and patients will return them in a pre-stamped envelope. Adherence will be defined as use of medications on #70% of days prescribed, a commonly applied convention.

Cognitive: Quick mild cognitive impairment screen (QMCI).

Lifestyle: physical activity, electronically measured: objective measurement using Actigraph. Physical activity adult questionnaire (PAAQ). Smoking/alcohol/drug activity. Activities of daily living questionnaire (ADL), general health (single item). Comorbidities (Charlson Index).

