Comprehensive Home-based Self-management Support for COPD Patients
PI: [name] [name]
NCT04533412
Document Date: 9-06-2021

STATISTICAL ANALYSIS PLAN

We compared the baseline characteristics of study participants in the intervention and control groups using a t-test, Wilcoxon Rank Sum test or chi-square test, as appropriate. We used a difference-in-differences (DiD) approach to examine the effects of intervention and control over time. Analyses were performed using generalized linear models with a REPEATED statement (SAS Proc GENMOD). As a feasibility trial, the study was not powered to detect statistically significant differences for outcomes between intervention and control arms, though $P < 0.05$ was considered statistically significant for all outcomes analyses. All analyses were performed using SAS software, version 9.4 (SAS Institute, Inc., Cary, NC).

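### At 29 patients per arm, GENMOD's default REPEATED inference (uncorrected sandwich SE, z test) gives a true type I error of about 5.9% for continuous outcomes, and the SAP states no correction

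*SAP*

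**What the plan says.** The SAP is a single paragraph. It sets the estimand, "We used a difference-in-differences (DiD) approach to examine the effects of intervention and control over time", then the tool: "Analyses were performed using generalized linear models with a REPEATED statement (SAS Proc GENMOD". It fixes the software, "All analyses were performed using SAS software, version 9.4", and states that P < 0.05 "was considered statistically significant for all outcomes analyses". It also says that "the study was not powered to detect statistically significant differences for outcomes between intervention and control arms".

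The sample size is in the Protocol, section 3(e), part B (Phase II): "We will randomize 58 COPD patients (29 per arm". Item g of the procedures gives the measurement times: "Baseline, 6- and 9-month interviews will be in-person or over the phone". Item j (Quantitative Data Analysis) says: "The primary outcomes are CAT score, ICS technique, and PAAQ scores at 9 months".

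Neither document names the link, the working correlation, the variance estimator, the test statistic, its reference distribution, the degrees of freedom or any small-sample correction. The SAP does not mention confidence intervals. Neither document gives an expected attrition rate.

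**The concern.** A REPEATED statement in GENMOD fits generalised estimating equations. Unless told otherwise, the procedure reports empirical (sandwich) standard errors and z statistics. Both are large-sample tools, where the number of patients is the relevant sample size, and here that is at most 29 per arm.

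Two approximations err in the same direction. The sandwich variance averages squared residuals over n where an unbiased estimate would use n − 1 in each arm. The z reference then treats that estimated variance as known. P-values come out too small and intervals too narrow. The bias is systematic and recurs for every continuous outcome analysed this way, against a threshold that the SAP applies to all of them.

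**Working it through.** **The plan's own figure.** The documents contain no power or sample-size calculation, so 58 cannot be reproduced. The only figure to test is the nominal 0.05. Its sidedness is not stated; two-sided is assumed.

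**Inputs.**
- n = 29 per arm (Protocol 3(e), part B).
- Three visits: baseline, 6 and 9 months (Protocol 3(e), item g).
- Contrast: difference between arms in change from baseline to 9 months (SAP for the approach, Protocol item j for the time point).
- Assumed, because the SAP is silent: arm-by-visit means, identity link, default sandwich SE, z reference.
- For the closed form: complete data, normal changes, equal variance in the two arms.

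**Step 1, standard error.** With complete data the sandwich variance of the contrast is the sum over arms of (sum of squared deviations of change / n) / n. The unbiased version has n − 1 in the inner denominator. The ratio of standard errors is therefore √((n − 1)/n). At n = 29 this is √(28/29) = 0.983, so the SE is 1.7% too small.

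**Step 2, type I error.** The reported z equals the ordinary two-sample t divided by that ratio. Rejecting when |z| > 1.960 is the same as rejecting when |t| > 1.960 × √((n − 1)/n), so

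size = P(|t on 2n − 2 df| > 1.960 × √((n − 1)/n)).

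At n = 29 the cut-off is 1.960 × 0.9826 = 1.926 on 56 df, and the size is 0.0592. With an unbiased SE and z alone, the size would be 0.055. The uncorrected sandwich adds the rest.

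**Step 3, interval width.** Relative to the t-based interval, width = 1.960 × √((n − 1)/n) / t(0.975, 2n − 2). At n = 29 this is 1.926 / 2.003 = 0.961. The interval is 3.9% too narrow and its coverage is 94.1%.

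**Step 4, assumed losses.**

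| Analysed per arm | df | SE ratio | Size | Width ratio |
|---|---|---|---|---|
| 29 | 56 | 0.983 | 0.0592 | 0.961 |
| 26 (assumed) | 50 | 0.981 | 0.0603 | 0.957 |
| 23 (assumed) | 44 | 0.978 | 0.0618 | 0.951 |
| 20 (assumed) | 38 | 0.975 | 0.0637 | 0.944 |

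**Step 5, simulation** (20,000 replicates, three visits, within-patient correlation 0.5, 9-month contrast, 29 per arm).
- Sandwich with z: 0.0586 with normal errors, 0.0596 with skewed errors.
- Joint 2-df Wald test of arm by time: 0.064.
- Score-type tests: 0.050 (1 df) and 0.048 (2 df).
- n/(n − 1) variance correction with t on 2n − 2 df: 0.049.

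A separate simulation fitted the estimating equations directly, with an exchangeable working correlation and assumed random dropout reaching 20% by the last visit. It gave 0.062 over 1,500 replicates (Monte Carlo SE about 0.006). Binary outcomes were not verified.

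**Step 6, which results would change.** A t of exactly 2.003 (correct P = 0.05) is reported as z = 2.003 / 0.9826 = 2.039, or P = 0.041. At 29 per arm, only results reported between about 0.041 and 0.05 would cross the line.

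**The case against.** The strongest objection is that the premise is a software default and not SAP text. GENMOD can also report model-based standard errors and score tests, and the score-type tests simulated at 0.048 to 0.050. A reader might infer that the 5% level is certainly missed for every continuous outcome. The documents do not support that, because they do not say which statistic supplied the P-values. This stands, and it makes the conclusion conditional. It does not remove the point. Nothing in the SAP departs from the default, and a score test would leave the printed standard errors and Wald intervals uncorrected.

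A reader might also infer that standard errors and intervals that are too small will be carried into the sizing of a later trial. No section says so. The forward use stated in Protocol item j's neighbour, item i (qualitative exit interviews), is to refine the intervention. The SAP plans no confidence intervals, so the width result applies only to intervals actually taken from this output.

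The third objection is size. The inflation is 0.9 percentage points, in a trial the SAP describes as unpowered for between-arm differences. The SE shortfall of 1.7% is small beside the sampling error of a standard deviation on 56 df, roughly 1/√112 = 9%. This stands as to importance. Low power is still no reason to accept an inflated error rate while keeping a P < 0.05 rule.

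Finally, a Gaussian mixed model does not suit every outcome. Protocol item j defines electronic adherence by a threshold on days of use, which is binary. That objection is right, and the fix allows for it.

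**Conclusion.** The point holds, conditionally and at modest size. If the named procedure is run at its default, the true two-sided type I error for a continuous outcome is about 5.9% at 29 per arm, and about 6.0% to 6.4% at 26 to 20 per arm. The corresponding SE is about 1.7% too small at 29 per arm, and any 95% interval about 4% too narrow.

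The closed-form figures rest on default sandwich-plus-z inference, arm-by-visit means, complete data among those analysed, and normal changes with equal variance. Simulation with skewed errors and with random dropout gave similar values. The loss range is assumed. The figures do not cover binary outcomes.

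This is more than a missing detail, because following the SAP literally leads to a mildly anti-conservative test. It does not invalidate the feasibility analysis. It is worth correcting, but it should not be presented as a major flaw.

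**What to change.** State the variance estimator, test statistic and reference distribution in the SAP, in place of the GENMOD default.

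- **Continuous outcomes:** use a mixed model with Kenward-Roger degrees of freedom, or a bias-corrected sandwich (for example PROC GLIMMIX with EMPIRICAL=FIRORES or MBN), with t-based tests and limits.
- **Binary outcomes**, such as thresholded adherence: use the bias-corrected sandwich with t-based inference.

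In the normal, equal-variance case the n/(n − 1) correction with t on 2n − 2 df brings the size back to exactly 0.05.

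The SAP is written in the past tense, so the cost is probably a small re-run and re-report of completed analyses. It needs no new data. P-values rise slightly, and intervals at 29 per arm widen by about 4% (2.003 / 1.926 = 1.04).
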